# **THE EFFECT OF STRESS BALL and MUSIC ON ANXIETY, STRESS, AND PAIN LEVELS DURING PLATELET APHERESIS DONATION: RANDOMIZED CONTROLLED TRIAL**

## **1. Introduction**

Platelet apheresis transfusion can be used for therapeutic or prophylactic purposes, primarily in oncology and hematology patients (1). Platelet apheresis donors may experience anxiety, stress, and pain due to the need for a wide-lumen vascular access site to ensure adequate blood flow, the complexity of the devices used during the procedure, and the need to keep a needle in the donor's arm for an average of 1 hour. There are numerous approaches, including pharmacological and non-pharmacological methods, to reduce these negative feelings (2). The use of non-pharmacological methods such as listening to music, squeezing a stress ball, watching a movie, using virtual reality glasses, daydreaming, and smelling lavender during invasive procedures has been shown to reduce anxiety, stress, and pain symptoms in individuals (3).

During invasive procedures, stress balls, which are inexpensive and accessible, have been observed to be used as a distraction and attention-grabbing method to reduce anxiety, stress, and pain (4,5,5). Listening to music is another non-pharmacological method that can alleviate anxiety, stress, and pain during invasive procedures. Listening to music before and during invasive procedures has been found to reduce systolic blood pressure, heart rate, and anxiety levels (7,8).

A review of the literature revealed no studies using squeeze ball therapy targeting the sense of touch and music listening targeting the sense of hearing to relieve anxiety, stress, and pain during platelet apheresis donation (PAD). In this context, this study aims to investigate the effects of applying a stress ball, a distraction-attention method, and listening to music, which targets the sense of hearing, on anxiety, stress, and pain levels in platelet apheresis donors, in addition to routine care. It is believed that the data obtained at the end of the study will provide evidence of the effect of stress balls and music listening used during platelet apheresis donation on anxiety, stress, and pain.

## **Research Hypotheses**

**H1:** There is a significant difference in anxiety levels between donors who receive routine care, use stress balls, and listen to music during PAD.

**H2:** There is a significant difference in stress levels among donors who receive routine care, use stress balls, and listen to music during PAD.

**H3:** There is a significant difference in pain levels among donors who receive routine care, use stress balls, and listen to music during PAD.

## **2. Materials And Methods**

### **Research Purpose and Design**

This study was a single-center, prospective, randomized controlled trial designed to investigate the effects of using stress balls, a distraction-attention method, and listening to music on anxiety, stress, and pain levels in PAD, in addition to routine care.

### **Research Population, Sample**

When determining the sample size, the effect size was calculated using results similar to a master's thesis (9). The sample size for the study was calculated using the G-power (v3.1.9.7) program with "effect size = 0.30, alpha = 0.05, power = 0.85, number of groups = 3, and number of measurements = 2" using ANOVA: Fixed effects, omnibus, one-way. The specified calculation yielded a minimum sample size of 93 donors, with 31 donors per group. 14 individuals who declined to participate, 15 who did not meet the inclusion criteria were excluded from the study. Taking all these losses into account, the study was completed with a total of 102 individuals, 34 in each study group.

The study included participants aged  $\geq 18$  and  $\leq 55$  who could read Turkish, had no physical limitations preventing them from squeezing a stress ball, had no psychiatric disorders, vision, hearing, or perception problems, met the platelet apheresis donation criteria according to the institutional protocol, were first-time platelet apheresis donors, voluntarily wished to donate platelets by apheresis, and voluntarily agreed to participate in the study.

Donors who withdrew from PAD, wished to leave the study, developed a reaction during donation, or were unable to complete the procedure due to insufficient blood flow through the catheter were not included in the study.

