## Ensuring Randomization

Platelet apheresis donors were randomly assigned to groups using a stress ball, music listening, and a random number table—a simple random sampling method—to minimize selection bias.

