## Data Collection Tools

Data were collected by researchers at a university hospital's blood transfusion center between August 1, 2024, and August 1, 2025. Donors were asked to complete questionnaire forms before and after PAD, a process that took approximately 10-15 minutes.

**Donor Information Form (DIF):** The researchers created the Donor Information Form, which contains a total of 14 questions. The form consists of two sections: socio-demographic characteristics and donor parameters. The first section contains questions about the donors' socio-demographic characteristics (age, gender, education level, occupation, family type, place of residence, and tobacco/alcohol use). The second section contains questions about donor characteristics (blood type information, previous blood donation, and degree of kinship with the recipient).

**Beck Anxiety Scale (BAS):** Measures the frequency of anxiety symptoms experienced by the individual. Beck and colleagues developed it and, it is a 21-item Likert-type self-assessment scale (10). The Turkish validity and reliability study was conducted by Ulusoy and colleagues (11). The sum of the scores is evaluated as follows: 0-7: Minimal anxiety, 8-15: Mild anxiety, 16-25: Moderate anxiety, 26-63: Severe anxiety. The total score is used in the evaluation of the scale, and an increase in the score indicates an increase in the level of anxiety (10).

**Distress Thermometer (DT):** Roth and colleagues developed it in 1998 to measure and evaluate the psychosocial distress experienced by cancer patients (12). Its validity and reliability in Turkish were established by Özalp and colleagues (13). “0” represents no distress, “10” indicates the highest level of distress. The cutoff point is 4 points, and it is recommended that patients with a distress level of 4 points or higher should receive professional support (12).

**Visual Analog Scale (VAS):** The Visual Pain Scale is a safe, valid, and easy-to-use tool for measuring pain repeatedly (14). Its validity and reliability in Turkish were established by Yaray and colleagues (15). “0” on the vertical or horizontal scale denotes no pain, while “10” signifies unbearable pain (14,15).

**Donor Monitoring Chart:** The form prepared by the researchers was used to record vital signs such as temperature, heart rate, blood pressure, respiratory rate, and oxygen saturation before and after the procedure.

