#### ***Stress Ball Group***

Ten minutes before PAD, DIF, BAS, DT, and VAS were completed as pre-tests during a face-to-face interview, and vital signs were recorded on the Donor Monitoring Chart (DMC). When the PAD procedure began, a stress ball was placed in the palm of one hand. Donors were instructed to squeeze the ball as often as they wished for a total of 30 minutes during the procedure. Five minutes after the donation was completed, the BAS, DT, and VAS were filled out as final tests. Vital signs were recorded on the DMC, and the study was concluded.

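### By rule the analysed donors are reaction-free completers, selected on events seen only after the assigned intervention begins; no as-randomised set is defined, and no numbers allocated or removed are given by arm.

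*Combined protocol and SAP*

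**What the plan says.** **Who is removed.** Research Population, Sample excludes two kinds of donor after the inclusion criteria: "Donors who withdrew from PAD, wished to leave the study", and those who "developed a reaction during donation, or were unable to complete the procedure due to insufficient blood flow through the catheter were not included".

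**Which losses are counted.** The same section reports that "14 individuals who declined to participate, 15 who did not meet the inclusion criteria were excluded from the study". It continues: "Taking all these losses into account, the study was completed with a total of 102 individuals, 34 in each study group". Neither count is split by arm, and the number randomised is not given.

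**When allocation happens.** Ensuring Randomization says "Platelet apheresis donors were randomly assigned to groups using a stress ball, music listening, and a random number table", with no time point. Implementation Phase says that each group had its own consent form, which suggests that the group was set at or before consent.

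**When the intervention starts.** In the Stress Ball Group section, "When the PAD procedure began, a stress ball was placed in the palm of one hand". In the Music Listening Group section, the music likewise starts after donation has begun.

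**When the outcome is taken.** In all three arms the post-test is timed at five minutes after completion.

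**What is analysed.** Statistical Analysis and Evaluation of Data lists tests and a significance level. It defines no analysis set and no rule for missing outcomes.

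**The concern.** Two of the four removal reasons are not eligibility criteria, because they are events that can follow exposure to the assigned arm. Withdrawal and leaving the study may fall before or after allocation, since the time of allocation is not stated.

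The rule and the outcome schedule also do not match. A donor who reacts but finishes has a scheduled post-test and is removed anyway. A donor who stops early has no scheduled post-test, because it is timed from completion.

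The outcomes under H1 to H3 are anxiety, stress and pain. A reaction, a withdrawal or a failed procedure could plausibly be related to any of them, although no section gives data on this. If removals came after allocation, differed by arm in number or in mechanism, and were related to the scores, the group comparison would partly reflect who was taken out. Without counts by arm, a reader cannot tell a bias of zero from a material one.

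**Working it through.** **1. The plan's own figures.** 3 x 34 = 102 completers, and 14 + 15 = 29 named losses. The number approached is not stated. Adding 29 to 102 gives 131, but only by assuming that there was no other loss, so it is not a check. The margin of 102 over the calculated minimum of 93, (102 - 93)/102 = 8.8%, does not help either, because the only losses listed are refusals and ineligibility.

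**2. Do equal arms show that nobody was lost?** Under unrestricted simple randomisation of 102 donors to three arms, P(34/34/34) = 102!/(34!^3 x 3^102) = 0.0081, about 0.8%. The exact balance fits a restriction, a quota or replacement that is not described. It proves none of these and does not show zero loss.

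**3. Mean shift in one arm.** *Assumption:* a fraction q = 5-10% is removed from one arm only, on a latent variable with correlation rho to the score. For a normal score the shift is rho x phi(z)/(1 - q), with z the upper-q normal quantile. For an exponential score (illustrative of skew) with the worst q removed, it is q x ln(1/q)/(1 - q).

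Reference effect: the plan's f = 0.30 with both active arms equal gives d = 0.30 x 3/sqrt(2) = 0.636 SD.

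| Dependence | q = 0.05 | q = 0.10 | Share of 0.636 SD |
|---|---|---|---|
| None (rho 0) | 0 | 0 | 0% |
| Weak (rho 0.3), normal | 0.033 SD | 0.059 SD | about 5-9% |
| Worst scorers (rho 1), normal | 0.109 SD | 0.195 SD | 17-31% |
| Worst scorers, exponential | 0.158 SD | 0.256 SD | 25-40% |

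**4. False-positive rate.** Simulation with 60,000 runs, no true effect, 34 analysed per arm, one-way ANOVA at 0.05, and removal by rank from one arm:

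| Dependence | 2 of 36 removed | 4 of 38 removed |
|---|---|---|
| None (rho 0) | 5.1% | 5.0% |
| Weak (rho 0.3) | 5.1% | 5.7% |
| Worst scorers, normal | 8.2% | 14.2% |
| Worst scorers, exponential | 10.6% | 20.9% |

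If the worst scorers are instead removed by a fixed score threshold at q = 0.05 or 0.10, the rates are 7.1% and 12.1% (normal) and 8.6% and 17.8% (exponential).

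**5. Is equal removal across arms safe?** Not always (normal score):
- Common score threshold in every arm: 5.0%.
- 2 or 4 removed per arm, on score in one arm and at random in the other two: 8.1% or 13.9%.
- Worst 2 or 4 by rank in every arm: no expected mean difference, but 7.6% or 9.7%, because the within-arm variance is understated.

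**6. How wide would bounds be?** With k donors removed from an arm with 34 analysed, giving them the best and then the worst score moves that arm's mean over range x k/(34 + k). The Distress Thermometer and VAS run from 0 to 10; the Beck scale runs from 0 to 63 ("0-7: Minimal anxiety, 8-15: Mild anxiety, 16-25: Moderate anxiety, 26-63: Severe anxiety").

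| k | DT or VAS: 10k/(34 + k) | Beck: 63k/(34 + k) |
|---|---|---|
| 1 | 0.29 | 1.8 |
| 2 | 0.56 | 3.5 |
| 4 | 1.05 | 6.6 |

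**The case against.** The strongest reply is that no removal is shown. The only losses named are refusals and ineligible donors, and the text goes from them straight to 102 completers. On that reading the rule was never used, the bias is zero, and the point is a request for one clarifying sentence. The reply adds that 5-10% removed from one arm comes from no section, that 8-14% needs exactly the worst scorers to be removed, that a latent correlation of 0.5 gives only 5.6% or 6.9%, and that no section links flow failure to the scores.

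Most of this stands. It limits the size of the point but does not remove it. The rule is written in the past tense as something applied, and no sentence says that it affected nobody.

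Three firmer readings are tempting, and the documents support none of them:
- **Donors were removed and the result is biased.** No section reports a removal, and the direction of any bias is unknown.
- **The exactly equal arms show that removed donors were replaced.** A restricted allocation or a quota would give the same balance.
- **The bias is zero because the 29 losses came before allocation.** Separate consent forms by group suggest that the group may have been known at consent, so even the 14 refusals may have followed allocation.

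**Conclusion.** The point holds as a defect of rule and reporting, not as a demonstrated bias. Followed as written, the plan compares groups selected on events after the intervention has begun, and its result applies only to donors who had no reaction and completed the donation. That allocation came before donation is inferred from the consent forms and the order of procedures; it is not stated outright.

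The size of any bias cannot be derived from the documents and may be zero. The illustrative range rests on an assumed 2 of 36 or 4 of 38 removed from one arm with no true effect. It runs from an essentially nominal 5-6% (no or weak dependence), through 8-14% (exactly the worst scorers), to 11-21% (the same with an exponential score). The upper figures are limits under strong assumptions, not estimates for this trial. The point should be fixed; confidence is medium.

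**What to change.** 1. **Report the flow by arm:** numbers allocated, refused after allocation, removed by reason (withdrew from donation, left the study, reaction, flow failure) and analysed. State when allocation took place. If no donor refused or was removed after allocation, say so; that closes the point.
2. **Otherwise, analyse all randomised donors in their assigned group** with every available post-test. Include donors who reacted but have a post-test, and leave out any who withdrew permission to use their data. Label this as a post hoc change, and keep the reaction-free completers result as a sensitivity analysis.
3. **Where removed donors have no post-test,** describe the result as applying to reaction-free completers and add the best/worst-score bounds by arm. Use imputation only if their pre-tests were kept, and state its missing-at-random assumption.

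**Cost.** Data collection is dated "between August 1, 2024, and August 1, 2025", so the cost is in analysis and reporting only. It is one sentence and a count by arm if nobody was lost. Otherwise it is one re-analysis and possibly wider intervals. The bounds are informative only for few losses: at four removed from one arm they already span about one point on the 0-10 scales. If no records of removed donors were kept, only the label and the bounds remain, and the bounds need at least the number removed by arm.

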## Ensuring Randomization

Platelet apheresis donors were randomly assigned to groups using a stress ball, music listening, and a random number table—a simple random sampling method—to minimize selection bias.

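### Allocation is described as simple random sampling with no restriction or concealment, yet exactly 34 donors completed in each arm, and the plan does not say how equal arms arose

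*Combined protocol and SAP*

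**What the plan says.** The protocol's section Ensuring Randomization is one sentence. It says allocation used a random number table, which it calls "a simple random sampling method", with the aim of limiting selection bias. It gives no allocation ratio, block size, stratification, list length, replacement rule, person holding the sequence, or means of concealing it.

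The section Research Population, Sample says the calculation "yielded a minimum sample size of 93 donors, with 31 donors per group" and then that "the study was completed with a total of 102 individuals, 34 in each study group". The only losses counted are these: "14 individuals who declined to participate, 15 who did not meet the inclusion criteria were excluded from the study". Both are categories that normally precede allocation. The same section leaves out donors who withdrew, left the study, had a reaction, or could not finish because of poor flow, but gives no numbers and no breakdown by arm.

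The section Implementation Phase says that consent was taken on a form prepared separately for each group. The group descriptions that follow place the pre-test of anxiety, distress and pain ten minutes before donation, by face-to-face interview.

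**The concern.** Read as unrestricted allocation, the stated method lets arm sizes drift, so identical arms are a surprising result. They are more surprising because 34 is a count of completers, after exclusions that nobody has counted. Some step that shaped the arms may therefore be missing from the plan.

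What is at stake depends on that step. With a quota, the last allocations can be foreseen by anyone who knows the running counts. With replacement of donors after allocation, the analysed groups are not the randomised groups. With a concealed list prepared in advance, neither problem arises.

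Concealment is the more important gap. If a donor signs a form specific to one group, both the donor and the researcher may know the arm before consent and before the self-reported baseline. That could influence who enters each arm and how the pre-test is answered. The section's own stated purpose is to limit selection bias.

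**Working it through.** **Inputs from the documents.** Total 102; arms 34/34/34; planned minimum 31 per arm (section Research Population, Sample). Method: random number table (section Ensuring Randomization). **Assumptions.** Equal 1:1:1 probabilities and independent allocations, that is, the unrestricted reading. The plan states no ratio.

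**The plan's own figure.** The documents give no probability for the achieved split. Their only calculated figure is 93 (31 per group). It does not reproduce: one-way ANOVA with the stated inputs (effect size 0.30, alpha 0.05, power 0.85, three groups) needs 126. That is a separate matter. Here 31 is used only as the plan's declared minimum.

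**Step 1. Chance of exact equality.**
P(34, 34, 34) = 102! / [(34!)³ × 3¹⁰²] = 0.00805, about 0.8%, or 1 in 124.

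**Step 2. Spread of arm sizes.**
SD of one arm = √(102 × 1/3 × 2/3) = √22.67 = 4.76. The central 95% range for one arm is 25 to 43. By simulation (1,000,000 runs), the median gap between largest and smallest arm is 9 (5th to 95th percentile 2 to 19), and a gap of 3 or less has probability about 10%.

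**Step 3. Chance of meeting the minimum.**
The sum of the multinomial probabilities over all splits of 102 with every arm at 31 or more is 0.348, about 35%.

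**Step 4. What a quota would do (assumed rule: each arm closes at 34).** In 20,000 simulated trials, on average 14.5 donors were allocated after the first arm closed. About 9.3 of them were still random between two arms, and 5.2 were fully determined (median 4; 5th to 95th percentile 1 to 12). The determined part is 5.2/102, about 5% of donors.

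**Step 5. Completers against allocated donors.** A balanced list makes the *allocated* numbers equal. Equal *completers* need in addition no later loss, equal loss in each arm, or replacement. As an illustration, if losses fall on the three arms independently with equal chance, the probability that they are equal is:

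| Losses (assumed) | Calculation | Probability |
|---|---|---|
| 3 | 3!/(1!)³ ÷ 3³ = 6/27 | 22% |
| 6 | 6!/(2!)³ ÷ 3⁶ = 90/729 | 12% |
| 9 | 9!/(3!)³ ÷ 3⁹ = 1680/19683 | 9% |

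The number of such losses is not reported and may be zero.

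**The case against.** The strongest reply is that the plan never uses the word unrestricted. Simple random sampling ordinarily means drawing a fixed number without replacement. Drawing 34 of 102 serial numbers per group from a table gives 34/34/34 every time, and the figures in steps 1 to 3 then do not apply. The sentence is also loosely written, so one phrase in it cannot bear much weight. This stands. A reader might infer that a quota or a replacement rule must have been used, but the documents do not support that. A fixed-size or blocked list explains equal allocation equally well, and 0.8% is not zero.

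A reader might also infer that any such rule makes allocation predictable or selective. That does not follow either. A concealed list prepared in advance is neither. A quota determines only the last few allocations, and only people who know the counts can exploit it. No post-allocation loss or replacement is reported, so replacement is one possibility among several.

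The gain from equal arms should not be oversold. With the plan's effect size and one-way ANOVA at 102 donors, power is about 0.766 with equal arms and about 0.760 on average under unrestricted allocation. Nor are small blocks a cure in themselves. With blocks of 3 and 6 used equally often, and with counts and block boundaries known, the determined allocations average 1 per block of 3 and 1.2 per block of 6, so (1 + 1.2)/9, about 24%. That exceeds the 5% under a quota. Concealment is what protects the allocation.

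The reply does not close the point. The fixed-size reading accounts for allocated donors, while the figure reported is completers, and the exclusions in between have no counts. It also says nothing about concealment or about the consent forms specific to each group.

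**Conclusion.** The concern holds as an undescribed allocation procedure. Exact 34/34/34 has probability 0.8% if 102 donors were allocated 1:1:1 without restriction, and under that reading the planned minimum of 31 in every arm would be met about 35% of the time. Both figures rest on the unrestricted reading, which the wording permits but does not compel. The plan does not say whether equal arms came from a fixed-size or blocked list, a quota, or replacement, and it gives no numbers randomised or excluded by arm.

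Concealment is not described, and the group-specific consent forms suggest, without proving, that the arm may have been known before consent and the pre-test. The documents do not show that allocation was manipulated or that any result is wrong. They leave a reader unable to judge whether selection bias was prevented. The design change is cheap and worth making in any repeat; for the finished study the remedy is disclosure.

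**What to change.** **For the plan, or any repeat of it.** In Ensuring Randomization, specify a restricted 1:1:1 list generated in advance, for example permuted blocks of randomly varied size that are not disclosed to enrolling staff. Hold it in sequentially numbered, sealed, opaque envelopes, each opened only after consent and after the pre-test. State that donors are not replaced after allocation. Amend Implementation Phase so that all donors sign one common consent form describing the three groups.

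**Cost.** A computer-generated list and a set of envelopes. One consent form must replace three. Without replacement, completer numbers may differ between arms by a few donors.

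**For the completed study.** The allocation cannot be redone, so the report should:
- state the rule that produced 34 per arm, and whether any donor was replaced;
- state whether allocation was concealed, and when the arm became known relative to consent and the pre-test;
- give the numbers randomised, excluded after allocation and analysed, by arm and with reasons;
- acknowledge possible selection bias if the arm was known before consent.

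This should need only existing records.
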